8.6 Safety Analyses

Safety analyses will be conducted on the safety population defined as those Subjects who enter the bronchoscopy suite for the initial Coil procedure. AE and SAEs will be summarized by treatment group based on MedDRA codes. Incidence rates through 6 months will be summarized for treatment and control groups. For coil treated subjects, events will also be summarized by relevant, discrete time periods including the Treatment recovery period (30 days from either treatment), as well as through the 12- and 36-month follow-up periods.

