	
Death, Led to serious deterioration in the health of the subject that either resulted in A life threatening illness or injury, or A permanent impairment of a body structure or a body function, or In-patient or prolonged hospitalization, or Medical or surgical intervention to prevent life-threatening illness or injury or permanent impairment to a body structure or a body function Led to fetal distress, fetal death or a congenital anomaly/birth defect.
 
Information on Specific Respiratory Events of interest will be collected and analyzed via event specific case report forms. These events of interest include:
 
 • COPD exacerbation • Hemoptysis • Pneumothorax • Lower Respiratory Tract Infection/Pneumonia • Tissue Reaction, Localized (a.k.a. Coil Associated Inflammatory Response Syndrome (CAIRS), also called Coil Associated Opacity (CAO) in the IFU)

Statistical Analyses:
	
The co-primary effectiveness endpoint will be analyzed on the intent-to-treat (ITT) population through the 6-month visit, using descriptive statistics to summarize results separately for treatment and control groups. No comparative inferential statistics will be conducted.

	
Safety analyses will be conducted on the safety population defined as those subjects who enter the bronchoscopy suit for the initial Coil

--	--

	
procedure. AE and SAEs will be summarized by Treatment group based on MedDRA codes. Incidence rates through 6 months will be summarized for treatment and control groups. Events will also be summarized by relevant, discrete time periods including the Treatment recovery period (30 days from either treatment).
 
Descriptive statistics will summarize percent change in FEV₁ as well as AEs and SAEs at 12 and 36 months follow-up for all coil treated subjects.

RESULTS	

Number of subjects to be analyzed
	
A total of 120 Subjects were randomized in a 2:1 ratio of Treatment to Control, respectively (80 Treatment group subjects, 40 Control group subjects).

Duration of the follow-up	Subjects will continue in the study through 36 months from first Coil implant. If Control subjects don't participate to crossover, they will exit the study immediately.
----------------------------------	--

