4.2.2 Exclusion Criteria

The study population will not include any subjects who have met any of the exclusion criteria.

1. Known sensitivity to drugs required for performing bronchoscopy or in whom bronchoscopic procedures are contraindicated
2. Evidence of active infection in the lungs
3. Hypersensitivity or allergy to nitinol (nickel-titanium) or its constituent metals
4. Clinically significant pulmonary fibrosis
5. Clinically significant, generalized bronchiectasis
6. Clinically significant bleeding disorders
7. Patient taking immunosuppressive drugs other than steroids (e.g., for the treatment of cancer, rheumatic arthritis, autoimmune disease, or prevention of tissue or organ rejection).
8. Primary diagnosis of asthma
9. Two (2) or more COPD exacerbations in the prior year, or 1 or more COPD exacerbations in the prior 3 months with indication for hospitalization assessment, according to GOLD 2017 recommendations⁴⁵.

³ The World Health Organization defines physical activity as any bodily movement produced by skeletal muscles that requires energy expenditure – including activities undertaken while working, playing, carrying out household chores, travelling, and engaging in recreational pursuits. For those with limited mobility, this should be done at least 2 days per week.

⁴ Global Strategy for the Diagnosis, Management and Prevention of COPD, Global Initiative for Chronic Obstructive Lung Disease (GOLD) 2018

10. Predominant small airways disease defined as significant bronchiectasis with sputum production (> 2 tablespoons daily) or significant bronchial wall thickening per High Resolution Computed Tomography (HRCT)
11. Percent Low Attenuation Area (%LAA) < 20% in the most damaged lobe of either lung.
12. Computed Tomography (CT) Imaging consistent with active pulmonary infection, significant interstitial disease or pleural disease
13. Severe bullous disease (defined by bulla > 1/3 of lung volume, or single bullous defect > 8cm) or significant paraseptal emphysema [defined by numerous large (>1cm) paraseptal defects in the target lobe comprising >5% of total lung volume].
14. , or Lung pathology of nodule not proven stable or benign Radiographic confirmation of atelectasis or other scarring/fibrosis in areas of intended Coil implant
15. Use of more than 20 mg/day prednisone (or equivalent dosage of a similar steroid) daily

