4.3 Subject Crossover

Control group Subjects will be eligible for crossover to Treatment as soon as possible. Control subjects will be eligible for crossover if they still meet all inclusion and exclusion criteria, and if the patient is deemed to benefit from the Coil treatment by the investigator, based on best medical judgment. Crossover subjects will continue in the study through 36 months from first Coil implant. If Control subjects do not crossover to treatment, they will exit the study immediately.

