7.1.1 Definitions of SAE/SADE/USADE/Device Deficiency

Serious Adverse Event (SAE)

An SAE is any untoward medical occurrence that:

- results in death;
- Led to serious deterioration in the health of the subject , that either resulted in
 - A life-threatening illness or injury, or
 - A permanent impairment of a body structure or a body function, or
 - In-patient or prolonged hospitalization, or
 - Medical or surgical intervention to prevent life-threatening illness or injury or permanent impairment to a body structure or a body function
- Led to fetal distress, fetal death or a congenital anomaly/birth defect.

Serious Adverse Device Effect (SADE)

An SADE is an adverse effect that has resulted in any of the consequences characteristic of a serious adverse event.

Unanticipated Serious Adverse Device Effect (USADE)

A USADE is a serious adverse device effect which by its nature, incidence, severity or outcome has not been identified in the current version of the risk analysis report

Device Deficiency

A device deficiency is an inadequacy of a medical device with respect to its identity, quality, durability, reliability, safety or performance. Device deficiencies include malfunctions, use errors and inadequate labeling.

A device malfunction is the failure of a medical device to perform in accordance with its intended purpose when used in accordance with the instructions for use.

⋮
SAE information will be collected throughout the study. SAEs will be recorded on the eCRF by the investigator or authorized designee. Event, date of onset, duration, serious/non-serious, anticipated/not anticipated, severity, relationship to the procedure/device, outcome, and action taken will be recorded. Additional information on specific events may be requested in the eCRFs. All events must be recorded in English. Any source documentation required to investigate SAEs for reporting must be translated to English.

NOTE: A planned hospitalization for a pre-existing condition, or a procedure required by the clinical protocol, without a serious deterioration in health, is not considered to be a SAE.

An anticipated SAE is any SAE, the nature or severity of which is identified in the IFU. Any other device related SAE will be considered an unanticipated adverse device effect (USADE).

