8.3 Analysis Populations and Sub-Groups

Intent to Treat Population (ITT) – All randomized Subjects, regardless of whether or not treatment was attempted.

Per Protocol Population (PP) - All randomized Subjects without major protocol deviations (see Section 10.9).

Safety Population - All randomized Subjects who enter the bronchoscopy suite for the initial Coil procedure.

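### The 6-month Control adverse event rates are based on a safety population that a Control can join only by crossing over to coils

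*Combined protocol and SAP*

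**What the plan says.** Section 8.3 defines the Safety Population as "All randomized Subjects who enter the bronchoscopy suite for the initial Coil procedure". Section 8.6 applies it to safety as a whole: "Safety analyses will be conducted on the safety population defined as those Subjects who enter the bronchoscopy suite for the initial Coil procedure". The Statistical Analyses row of the synopsis repeats the rule ("defined as those subjects who enter the bronchoscopy suit for the initial Coil" procedure). No separate safety set for Controls appears anywhere in the protocol.

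Within the same paragraph, Section 8.6 plans a by-arm output: "Incidence rates through 6 months will be summarized for treatment and control groups". Its next sentence turns to coil-treated subjects and adds summaries for the recovery period and for the 12- and 36-month follow-up. The by-arm rates are therefore distinct from the coil-only summaries, but both are given the same population.

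Crossover is conditional. Section 4.3 says "Control subjects will be eligible for crossover if they still meet all inclusion and exclusion criteria", and adds the requirement "if the patient is deemed to benefit from the Coil treatment by the investigator". Controls who do not cross over leave the study (Sections 4.3, 5.1.4 and 6.4.4). By contrast, effectiveness is summarized on the ITT population, which Section 8.3 defines as everyone randomized, treated or not.

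**The concern.** Safety is part of the primary objective (Section 3.1.1), and the Control column is the untreated reference for the coil arm's event rates. Entry to the coil suite is a sensible gate for people assigned to coils. For Controls it selects on what happened after randomization: they must be alive, still eligible and judged suitable for the procedure.

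That selection can be tied to the events being counted. One exclusion criterion in Section 4.2.2 is "Two (2) or more COPD exacerbations in the prior year", and Section 7.2 lists COPD exacerbation as a respiratory event of interest. A Control whose exacerbations during follow-up make them ineligible for crossover drops out of the table meant to count those exacerbations. Section 7.1.1 classes as serious any event that "results in death", yet a Control who dies before coils can never enter the population in which serious events are tabulated.

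Treatment subjects face a much lighter gate: a first procedure due within 45 days of baseline (Section 5.1.3). The two columns would be printed side by side although they describe differently selected people.

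**Working it through.** **The plan's own figure.** Section 8.1 gives 120 subjects randomized 2:1. 120 × 2/3 = 80 Treatment and 120 × 1/3 = 40 Control, which agrees. The plan gives no size for the Safety Population and no crossover, event or death rate.

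**What the definition does.**
1. Safety analyses use only randomized subjects who reach the suite for a first coil procedure (8.3, 8.6, synopsis).
2. A Control gets there only through crossover (4.3).
3. So if m of the 40 Controls never cross over, the Control denominator is 40 − m, and every Control counted is a crossover.
4. The same rule removes any Treatment subject who was randomized but never reached the suite.

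**Size for events in general.** Let rc be the event rate in Controls who cross over and rn the rate in those who do not. The rate over all Controls is [(40 − m)·rc + m·rn]/40. The reported rate is rc, so

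reported − all-randomized = (m/40) × (rc − rn).

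The values of m, rc and rn below are assumptions.

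| m | denominator | rc | rn | all 40 | reported | difference |
|---|---|---|---|---|---|---|
| 4 | 36 | 20% | 50% | 23% | 20% | −3 points |
| 8 | 32 | 20% | 50% | 26% | 20% | −6 points |
| 20 | 20 | 20% | 50% | 35% | 20% | −15 points |
| any of these | 40 − m | 20% | 20% | 20% | 20% | 0 |

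If rc exceeds rn, the sign reverses.

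**Logical limits.** Suppose 16 of 40 Controls had an event (16/40 = 40%, assumed). The reported rate is lowest when all m non-crossers had events, (16 − m)/(40 − m), and highest when none did, 16/(40 − m).
- m = 5: 11/35 = 31.4% to 16/35 = 45.7%.
- m = 10: 6/30 = 20.0% to 16/30 = 53.3%.

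**Deaths before coils.** Each such death leaves both numerator and denominator. If the only Controls missing are those who died, one death turns 1/40 = 2.5% into 0/39, and two turn 2/40 = 5% into 0/38. If crossover happens only at month 6, Control deaths through month 6 are zero by construction. If it can happen earlier, the only Control deaths that could appear are those after coils.

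**The case against.** Section 8.2 leaves detailed methods and tables to a separate SAP, and Section 9 says analysis follows it. The SAP was not available and may define a Control safety set. That the plan has a Control column at all suggests the suite-entry rule may have been meant only for coil-treated subjects. Both points are fair, but the protocol says neither, and an SAP using all randomized Controls would contradict 8.3, 8.6 and the synopsis. The protocol wording would still need correcting.

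The analysis is descriptive (8.5), so no test or power is affected. That stands. It does not remove the problem, because with no inference planned the printed rates are the result.

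The sizes above are assumed, and the 31% to 46% and 20% to 53% ranges are extremes. That also stands. A reader might infer that the Control rates will be understated and the coils made to look worse. The documents support this only for deaths before coils. For other events the sign depends on whether non-crossers had more or fewer events than crossers. They may have had more if ill health barred them, or fewer if they felt well and declined.

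A reader might also infer that early crossover has contaminated the 6-month comparison or cost the study its untreated 6-month FEV₁ and SGRQ values. The crossover wording does conflict, but the documents do not establish that consequence. Randomization is described in the past tense (3.3, 6.1, 6.5.10, 8.1) and the current visit schedule has no 6-month visit, so this reads as an amendment written after randomization. Every Control may already have passed month 6. Sections 6.2 and 8.5 still refer to 6-month data, so the question stays open.

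**Conclusion.** The point holds as a defect in the written definition. Followed literally, 8.3, 8.6 and the synopsis produce a Control column made up only of crossovers, with every non-crosser missing and no Control death before coil treatment able to appear. This follows from the text and needs no assumption about rates.

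The impact cannot be sized from the documents. The bias is the fraction of Controls who never cross over times the difference in event rates between crossers and non-crossers. It is zero if those rates are equal or if everyone crosses over. Only the loss of untreated deaths has a fixed direction. The wording should be corrected because safety is a primary objective and the correction is cheap; the documents do not show that any reported rate is wrong. The conclusion is limited to the protocol text, since the SAP was not seen.

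**What to change.** In 8.3, 8.6 and the synopsis:

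1. Base the by-arm 6-month AE and SAE incidence on all randomized subjects in both arms, counted from randomization to month 6. Changing only the Control arm would set all randomized Controls beside treated-only Treatment subjects and create a new imbalance.
2. Cut Controls off at first coil procedure if that comes before month 6, and move their later events to the coil-treated summary. Where this shortens follow-up, also give events per patient-month.
3. Keep the suite-entry population only for coil-treated summaries (recovery period, 12 and 36 months).
4. Report how many subjects in each arm never entered the suite, with reasons.

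Consistency note: crossover is set at 6 months after entry in the synopsis Design row and the first paragraph of 3.2. The synopsis timelines row, the second paragraph of 3.2, and Sections 4.3 and 5.1.4 allow it without delay. State one rule, or state that all Controls have already passed month 6.

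The cost is wording and one revised table, provided the Control events were recorded. The synopsis says safety information is collected throughout the study. However, the current schedule lists AE review only at the two procedures and at 12 and 36 months, and non-crossing Controls exit. Pre-coil Control events may therefore rest on data already gathered or on unscheduled reports, and the sponsor should confirm what is held. The Treatment column would also include the short wait before the first procedure; the coil-treated summaries still show events by time since treatment.

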7.2 Recording Adverse Events (AE)

Subjects will be required to report AEs of interest. At each study visit, site staff will ask general, open-ended, non-directed questions to obtain information about AEs. If the subject is unable to attend a trial visit, AEs can be collected by telephone contact. At any time during the study, the Subject may volunteer information that meets the definition of an AE.

The investigator should record all SAEs and specific Respiratory AEs of interest in the eCRFs. Below is a list of specific Respiratory AEs of interest that should be recorded:

- COPD Exacerbation
- Hemoptysis
- Pneumothorax
- Lower Respiratory Tract Infection/Pneumonia
- Tissue Reaction, Localized (a.k.a. Coil Associated Inflammatory response syndrome (CAIRs), also called Coil Associated Opacity (CAO) in the IFU)

Investigators will obtain all the information required to complete the AE form. Where possible, a diagnosis, rather than a list of signs or symptoms, should be recorded. Any medical management of an event and the resolution of an event must be recorded in source documentation and on the appropriate eCRF using medical terminology according to sponsor instructions.

For each SAE and specific respiratory AEs of interest, the following information will be recorded at a minimum:

- AE term
- Serious/non-serious
- Severity
- Action taken
- Relationship to Coil System
- Expected/Unexpected
- Date and time of onset
- Date and time of resolution

Was the subject withdrawn from the study due to the AE

Any SAE experienced by a subject will be followed until the SAE has resolved to the PI's or sub-investigator's satisfaction or is considered stable. If a problem still exists, then the PI or sub-investigator at his/her discretion will ask the subject to come back to the clinic for further evaluation. SAEs should be managed as discussed in Section 7.5.

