7.7 Expected Adverse Events

AEs reported through clinical studies and post-market vigilance (in the EU and OUS regions) are detailed in the IFU. AEs which may be observed with endobronchial devices, systems for placement of these devices, and related procedures (including diagnostics and bronchoscopy procedures) and use of the Coil System include, but are not limited to, the events shown below. These events may vary in frequency and severity.

- Allergic Reaction
- Emphysema, Subcutaneous
- Pneumonia*
- Aspiration
- Hemoptysis, including Severe Hemoptysis
- Pneumonitis
- Bleeding or Hemorrhage
- Hoarseness
- Pneumothorax
- Bronchial Blood Clot
- Hypertension
- Procedure-Related Complication (e.g., fever, spasm)
- Bronchial Ulceration
- Hypotension
- Pulmonary Embolism

- Bronchospasm
- Cardiac Arrhythmias
- COPD Exacerbation
- Cough
- Death
- Device Dislocation
- Dyspnea
- Infection
- Inflammation
- Lung Abscess
- Pain
- Painful Respiration
- Pleural Effusion
- Pleural Fistula
- Respiratory Distress
- Respiratory Failure
- Respiratory Tract Infection
- Sedation – Related Complications (e.g., nausea, vomiting, headache)
- Sepsis
- Tissue Reaction, Localized (a.k.a CAIRs/CAO)
- Tissue Trauma, Procedural (e.g., tissue perforation, dissection)

*A recognized, non-infectious localized tissue reaction, also termed Coil Associated Inflammatory response syndrome (CAIRs), also called Coil Associated Opacity (CAO) in the IFU, may occur in the area of implanted coils and is typically diagnosed on imaging (chest X-ray or CT scan). This is believed to be an inflammatory response that presents with pneumonia-like symptoms, including chest or pleuritic pain/discomfort, increased dyspnea, fatigue, and/or haze or infiltrates on chest X-ray, and may be difficult to distinguish from pneumonia. While some degree of CAIRs/CAO has been observed in clinical trials up to 2 months following the Coil procedure, many of these events are asymptomatic or symptomatically mild, resolve with limited intervention, and do not develop into serious adverse events (SAEs). However, CAIRs/CAO can become severe and require prompt and specific intervention. Thus, subjects are advised to contact their treating physician immediately for follow-up if they experience pneumonia-like symptoms.

Note: Additional interventional procedures may be necessary if subjects experience some of these potential AE(s) following Coil treatment.

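### Pneumonia and the coil-associated tissue reaction (CAIRS/CAO) are counted separately though hard to tell apart, so the by-arm pneumonia incidence is open to labelling bias of unknown direction; a supplementary combined row is needed

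*Combined protocol and SAP*

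**What the plan says.** Section 7.2 and the synopsis name five respiratory events of interest. Two of them are "Lower Respiratory Tract Infection/Pneumonia" and "Tissue Reaction, Localized (a.k.a. Coil Associated Inflammatory response syndrome (CAIRs), also called Coil Associated Opacity (CAO) in the IFU". The synopsis adds: "Information on Specific Respiratory Events of interest will be collected and analyzed via event specific case report forms". On recording, Section 7.2 instructs: "Where possible, a diagnosis, rather than a list of signs or symptoms, should be recorded".

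Section 7.7 places CAIRS/CAO in the region of the implanted coils and calls it non-infectious. It continues: "This is believed to be an inflammatory response that presents with pneumonia-like symptoms". It lists shadowing on the chest film among the features and concedes that the condition "may be difficult to distinguish from pneumonia". The footnote that says this is attached to the pneumonia entry in the list of expected events.

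Section 8.6 sets the tabulation: "AE and SAEs will be summarized by treatment group based on MedDRA codes", and "Incidence rates through 6 months will be summarized for treatment and control groups". For coil-treated subjects it adds summaries for the 30-day recovery period and through 12 and 36 months. Section 3.2 describes the trial as open label.

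The text available contains no criteria for separating the two diagnoses, no blinded adjudication of events and no combined category. Section 8.2 leaves detailed tables to a separate SAP.

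**The concern.** The same clinical picture has one available label in a subject without coils and two in a subject with coils. The person choosing the label knows which kind of subject it is. The pneumonia row may therefore not measure the same thing in the two arms.

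The exposed period is long. Section 7.7 reports CAIRS/CAO up to 2 months after a procedure, and Section 5.1.2 places the two procedures about 2 months apart. If the 6-month window runs from the first procedure, about 2 + 2 = 4 of its 6 months are affected.

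The primary objective includes confirming the safety profile, and Section 8.6 names no safety test. The descriptive rates are thus the safety evidence. A reader who takes the pneumonia row at face value cannot tell how much of any difference, or lack of one, comes from labelling.

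**Working it through.** The documents state no pneumonia rate, CAIRS/CAO rate or error rate, so there is no planned figure to reproduce. The check asks how far labelling alone could move the pneumonia row.

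**Inputs from the documents:** 80 Treatment and 40 Control subjects (Section 8.1).

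**Assumed inputs:**
- p = true pneumonia incidence, equal in both arms: 5% to 20%
- c = true CAIRS/CAO incidence in Treatment: 10% in the main example, 5% to 20% for the break-even
- f = share of pneumonia labelled CAIRS/CAO in coil subjects: 0 to 0.5
- g = share of CAIRS/CAO labelled pneumonia: 0 to 0.5
- Control subjects have no coils during the window, each subject has at most one of the two events, and errors occur only between these two labels.

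**Formulas:**
- Observed Treatment pneumonia = p(1 − f) + c·g
- Observed Control pneumonia = p
- Bias in the Treatment row = c·g − p·f
- Combined row in Treatment = p + c, whatever f and g are
- The bias is zero when g = p·f/c

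**Results for p = 10%, c = 10%** (Control 4/40 = 10% throughout):

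| f | g | Treatment pneumonia row | Bias (points) | Combined row |
|---|---|---|---|---|
| 0.50 | 0 | 5.0% (4/80) | −5.0 | 20% (16/80) |
| 0.25 | 0 | 7.5% (6/80) | −2.5 | 20% (16/80) |
| 0.25 | 0.25 | 10.0% (8/80) | 0 | 20% (16/80) |
| 0.25 | 0.50 | 12.5% (10/80) | +2.5 | 20% (16/80) |
| 0 | 0.50 | 15.0% (12/80) | +5.0 | 20% (16/80) |

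**Other pneumonia rates, c still 10%:**
- p = 20%, f = 0.5, g = 0: 0 − 0.20 × 0.5 = −10 points.
- p = 5%, f = g = 0.25: 0.10 × 0.25 − 0.05 × 0.25 = +1.25 points.
- Over the assumed ranges the bias runs from −10 to +5 points.

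**Break-even for p = 10%, f = 0.25:** g = 0.025/c, which is 0.50, 0.25 and 0.125 for c = 5%, 10% and 20%. The sign thus depends on quantities that the documents do not give.

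**Scale:** at 10% in both arms the standard error of the difference is √(0.09/80 + 0.09/40) = √0.003375 = 5.8 points. A labelling shift of 5 points is about as large as the sampling error.

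**The case against.** A reader might infer that the pneumonia comparison *is* biased in favour of Treatment. The documents do not support that. The admitted difficulty in Section 7.7 works both ways: CAIRS/CAO recorded as pneumonia raises the Treatment row. A calculation that starts from all pneumonia-like events and treats each CAIRS/CAO label as a loss sets the reverse error to zero and counts correct diagnoses as mistakes. For example, if 20% of Treatment subjects have a pneumonia-like event and a quarter of those truly are CAIRS/CAO, a pneumonia row of 15% is right.

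Three other strong readings also go too far.
- Section 7.2 asks for a diagnosis where one can be made; it does not make the two terms mutually exclusive.
- CAIRS/CAO is itself an event of interest, so relabelled events move to another reported row and do not vanish.
- The CAIRS/CAO row is empty in Control only before coil treatment. Section 3.2 gives both 6 months after entry and as soon as possible for crossover, Section 4.3 gives as soon as possible, and Section 5.1.4 allows it immediately.

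The best argument against the remedy concerns ascertainment. Section 7.7 says that many CAIRS/CAO cases are mild or cause no symptoms and that the diagnosis typically rests on imaging. The schedule of visits places chest films at the coil procedures and has none for Controls between baseline and crossover. A combined row used as the main comparison would therefore tilt against Treatment. This stands, and it limits the row to a supplementary place.

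The separate SAP may also already contain such a row. That cannot be excluded, but nothing in the available text provides it.

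**Conclusion.** The point holds as a risk of bias of unknown sign, confined to how events divide between two reported rows. It rests on the documents' own statements: two separate events, an admitted difficulty in telling them apart, a label tied to coils, and open-label recording with no adjudication described. Its size rests wholly on assumed rates. In the main example the Treatment pneumonia row can be up to 5 points too low or too high, and the combined row is unaffected.

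That stability requires that errors pass only between the two labels; an event recorded as something else, such as an exacerbation, would still be lost. Two separate rows cannot replace the combined one, because a subject may appear in both and the number with at least one event cannot be recovered from them.

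No test or decision rule depends on the pneumonia row, so this is a cheap improvement to the safety tables and not a flaw that undermines the trial.

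The by-arm version has a prior condition. Sections 8.3 and 8.6 restrict the safety population to subjects who enter the bronchoscopy suite for a first coil procedure, so Controls enter it only through crossover. The 4/40 used above has no place under that definition until it is reconciled with the planned Control summary.

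**What to change.** In Section 8.6 and the synopsis, pre-specify a supplementary row, *LRTI/Pneumonia or CAIRS/CAO*, giving subjects with at least one event and the number of events, for all events and for serious events. Show it beside the two component rows, not in place of them, in the 6-month by-arm summary and in the coil-only 30-day, 12-month and 36-month summaries. State that the by-arm contrast is to be read mainly on serious events, because imaging at the coil procedures can reveal mild CAIRS/CAO for which Controls are not examined before crossover.

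Reconcile the safety population in Sections 8.3 and 8.6 with the by-arm summary, and the crossover timing across Sections 3.2, 4.3 and 5.1.4, so that the Control denominator and its coil-free time are defined.

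The row needs no new data: both events are already collected on event-specific forms. Its costs are that it mixes an infectious with a non-infectious event and that its all-events version remains open to ascertainment differences. The retained component rows address the first, and the emphasis on serious events limits the second.

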3 TRIAL OBJECTIVE(S)

3.1 Trial Objectives

3.1.1 Primary Objectives

The primary objective of the ELEVATE study is to prospectively confirm the safety and effectiveness profile of Coils for the treatment of severe emphysema in consideration of the findings of previous randomized controlled trials.

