3.3 Randomization

A total of 120 subjects were randomized in a 2:1 ratio of Treatment to Control respectively (80 Treatment group subjects, 40 Control group subjects) across up to 30 sites.

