3.4 Primary Endpoint (s)

The Co-Primary Effectiveness Endpoint for the study is:

- Percent change in FEV₁ from baseline to 6 months
- Change in St. George's Respiratory Questionnaire (SGRQ) from baseline to 6 months.

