8 STATISTICAL CONSIDERATIONS

8.1 Trial Design and Determination of Sample Size

A total of 120 Subjects were randomized in a 2:1 ratio of Treatment to Control respectively (80 treatment group subjects, 40 Control group subjects).

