8.5 Efficacy Analyses

All effectiveness analyses will be analyzed on the ITT population through the 6-month visit, using descriptive statistics to summarize results separately for treatment and control groups. No comparative inferential statistics will be conducted. In addition, descriptive statistics will summarize percent change in FEV₁ from baseline to 12 and 36 months for all coil treated subjects. Baseline will be defined as the last measurement taken prior to coil treatment.

Descriptive statistics will summarize effectiveness endpoints at 12, 24 and 36 months follow-up.

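### Confirming safety is part of the primary objective, but the supplied text plans incidence summaries with no measure of precision, and at most 120 coil-treated subjects leave rare events poorly bounded

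*Combined protocol and SAP*

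**What the plan says.** Section 3.1.1 names safety alongside effectiveness in the primary objective: to "prospectively confirm the safety and effectiveness profile of Coils for the treatment of severe emphysema", taking earlier randomised trials into account. Section 3.4 names endpoints for effectiveness only ("The Co-Primary Effectiveness Endpoint for the study is", followed by FEV₁ and SGRQ).

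For safety, section 8.6 plans AE and SAE summaries by group using MedDRA codes, and states that "Incidence rates through 6 months will be summarized for treatment and control groups". For coil-treated subjects it adds summaries for the 30-day recovery period and through 12 and 36 months. The Statistical Analyses entry of the synopsis says much the same. Neither place gives an interval, a precision target or a reference rate.

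Section 8.3 defines the safety population as "All randomized Subjects who enter the bronchoscopy suite for the initial Coil procedure". Section 8.1 gives the numbers randomised, "80 treatment group subjects, 40 Control group subjects", without a rationale. The sentence "No comparative inferential statistics will be conducted" stands in section 8.5 on efficacy and in the effectiveness paragraph of the synopsis. Section 8.6 does not repeat it.

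**The concern.** An objective of confirming a safety profile calls for some statement of how precisely the event rates are known. A percentage from a group of this size, printed without a limit, does not separate an event that is truly rare from one that the study was too small to show. Section 7.7 lists serious possibilities such as death, respiratory failure, sepsis and pulmonary embolism. If any of these is uncommon, a bare 0% or 1% says little without its upper limit.

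The denominators add to the difficulty. Controls are part of the safety population only if they enter the bronchoscopy suite, so a control rate computed on that population leaves out everyone who never crossed over.

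**Working it through.** **Inputs.** Numbers randomised: 120, split 2:1 (sections 3.3 and 8.1). Safety population: section 8.3. The 95% level, the event counts and the smaller denominators below are assumptions, because the documents give none.

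**The plan's own figure.** 120 × 2/3 = 80 and 120 × 1/3 = 40, as stated. The total of 120 cannot be re-derived, since no event rate, power or precision target is given.

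**Denominators.** Treatment subjects in the safety population: at most 80. All coil-treated subjects, if every Control crossed over: at most 80 + 40 = 120. Controls in the safety population: only those who cross over, a number not given.

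**Zero events.** The exact (Clopper-Pearson) two-sided 95% upper limit is 1 − 0.025^(1/n). The chance of seeing no event when the true risk is p is (1 − p)^n.

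| n | Upper limit with 0 events | No event seen, p = 1% | No event seen, p = 2% |
|---|---|---|---|
| 120 (maximum, all coil-treated) | 3.0% | 30% | 9% |
| 80 (maximum, Treatment) | 4.5% | 45% | 20% |
| 72 (assumed) | 5.0% | 49% | 23% |
| 64 (assumed) | 5.6% | 53% | 27% |
| 40 (all randomised Controls) | 8.8% | 67% | 45% |

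For example, 1 − 0.025^(1/80) = 0.0451 and 0.98^80 = 0.199.

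**Few events.** With x events, the lower limit is the 2.5% point of Beta(x, n − x + 1) and the upper limit is the 97.5% point of Beta(x + 1, n − x).

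- 1/80 = 1.25%: 0.03% to 6.8%
- 2/80 = 2.5%: 0.3% to 8.7%
- 8/80 = 10%: 4.4% to 18.8%
- 1/40 = 2.5%: 0.06% to 13.2%

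**Control group.** Read literally, section 8.3 puts only crossed-over Controls in the safety analysis. If 32 or 20 of them crossed over (assumed), the zero-event upper limit would be 10.9% or 16.8%. Width is the lesser problem. A Control who dies before crossover never enters the suite, and section 4.3 requires the eligibility criteria still to be met at crossover. Pre-crossover control deaths on that population are therefore zero by construction, and an interval would not show this bias. Using all 40 randomised Controls removes it.

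**The case against.** The strongest reply is that section 8.2 defers methods, tables and listings to a separate SAP, which may already contain intervals. That stands as a limit on the claim: the gap is shown for section 8.6 and the synopsis only. One confirming sentence would close that part of the point.

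A second reply is that anyone with a count and a denominator can work out an exact interval. This is true if both are printed, but the plan does not commit to stating denominators by group and period, and most readers will not do the calculation.

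Third, the objective refers to earlier randomised trials, and section 2.3 cites over 2,000 previously studied subjects. A reader might infer that the plan intends zero counts to be taken as proof of safety. No passage says so, and the study does not claim to exclude rare events by itself. The risk of over-reading is a fair inference from the word confirm, and no more than that.

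A reader might also infer that section 8.6 reports on 80 and 40 subjects. Those are the numbers randomised, so they are upper bounds for the safety population.

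Finally, the bar on comparative inference might be raised against the fix. It is written for effectiveness, and an interval within one group compares nothing. A Treatment-minus-Control interval is different: on the safety population as defined it would put a formal interval around a selection effect, and the co-primary endpoints would have no counterpart.

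**Conclusion.** The point holds in a limited form and should be acted on. The supplied text makes confirming safety part of the primary objective and commits to no measure of precision for it. At the largest denominators possible, a zero count leaves true rates of up to 4.5% (80 Treatment subjects) or 3.0% (120 coil-treated) compatible with the data, and smaller denominators leave more. These figures assume two-sided 95% exact limits and complete follow-up. They are limits on what the data could show and predict nothing about the result.

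The documents do not support saying that no intervals will be produced anywhere, or that a primary safety endpoint must now be added. The SAEs and the five respiratory events of interest are already specified (section 7.2 and the synopsis), so intervals on them select no endpoint and set no pass mark.

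**What to change.** In section 8.6 and the synopsis:

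- State the actual denominator for each group and period.
- Report the incidence of any SAE, of death and of each of the five respiratory events of interest with an exact (Clopper-Pearson) 95% interval, giving the upper limit when the count is zero. Do this by group at 6 months, and at 12 and 36 months in coil-treated subjects.
- At 12 and 36 months, state the number followed and how subjects with incomplete follow-up are counted.
- Compute the Control 6-month rate and its interval on all randomised Controls, using events before any crossover. Section 3.2 describes crossover both as six months after entry and as soon as possible, so also state how many Controls were still observed without coils at six months.

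A Treatment-minus-Control difference with an interval is optional. If given, it should be labelled as estimation only and use that corrected control denominator.

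The cost is a short paragraph, a rule for incomplete follow-up and extra table columns. No new visits or data are needed. The downside is that the safety statements will look less certain. If the separate SAP already specifies these intervals, a cross-reference is enough for that part, but the control denominator still needs correcting.
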